11.5.4. Efficacy

11.5.4.1. SELENA SLEDAI Disease Assessment Scale

11.5.4.2. BILAG

CCI - This section contained Clinical Outcome Assessment data collection questionnaires or indices, which are protected by third party copyright laws and therefore have been excluded.

CONFIDENTIAL

[figure not shown]
BEL114333

	Domain										Endpoint	
	1	2	3	4	5	6	7	8				
Belimumab Visit	General	Mucocutaneous	Neurological	Musculoskeletal	Cardiovascular/ Respiratory	Vasculitis	Renal	Hematology	New A or New B Compared to Baseline	BILAG (SRI) component (No new A and at most 1 new B)	BILAG 1A/2B Flare (At least 1 new A and/or at least 2 new B)	BILAG 1A Flare (At least 1 new A)
Baseline	Α	В	E	E	D	E	D	E	1A, 1B			
Year 1 Week 24	A	В	E	E	D	E	D	E	- IA, ID	√	×	×
Year 1 Week 48	В	В	E	E	D	E	D	E	-	✓	×	×
Year 2 Week 24	A	В	TE	C	В	E	D	E	1 new B	√	×	×
Year 2 Week 48	Α	В	В	С	D	E	D	Е	1 new B	√	×	×
Year 3 Week 24	D	В	В	С	В	Е	D	Е	2 new B	×	✓ (1st event)	×
Year 3 Week 48	Α	С	С	С	D	E	D	Е	-	✓	×	×
Year 4 Week 24	В	В	В	С	В	E	D	Е	2 new B	×	✓	×
Year 4 Week 48	Α	Α	С	С	D	Е	D	Е	1 new A	×	✓	✓ (1st event)
Year 5 Week 24	Α	Α	В	В	D	Е	D	E	1 new A, 2 new B	×	✓	✓
Year 5 Week 48	D	Α	Α	С	В	Е	D	Е	2 new A, 1 new B	×	✓	✓
Year 6 Week 24	Α	Α	Α	В	В	E	D	Е	2 new A, 2 new B	×	✓	✓
Year 6 Week 48	Α	Α	В	В	В	E	D	E	1 new A, 3 new B	×	✓	✓

11.5.4.3. Physician's Global Assessment (PGA) Score

- The PGA is collected on a 10 cm visual analogue scale (VAS).
- The standard scoring range for the PGA is 0 to 3, and the score will be rescaled for standard reporting by multiplying the collected score by 3/10. This re-scaling is applied in the eCRF data extraction.

[figure not shown]
11.5.4.4. SLICC/ACR Damage Index

11.5.4.5. SLE Flare Index

CCI - This section contained Clinical Outcome Assessment data collection questionnaires or indices, which are protected by thir party copyright laws and therefore have been excluded.	d
party copyright laws and therefore have been excluded.	

11.5.4.6. Spot Urine Protein Creatinine Ratio Conversion

Spot Urine Protein Creatinine Ratio

Conversion from mg/mmol to mg/mg (performed by central laboratory)

- For analysis, spot urine protein creatinine ratio (PCR) will be reported in mg/mg (or equivalently, g/24h).
- The SI unit for PCR is mg/mmol (which is the same as g/mol as stored in the database).
- To convert lab values reported as mg/mmol to mg/mg, divide the lab value by 113.12

Spot Urine Protein Creatinine Ratio

Example: (20 g/mol) / 113.12 = 0.1768 mg/mg

11.5.5. Biomarkers

Biomarker Parameters

Anti-ds DNA

- Positive: ≥30 IU/mL
- Negative: <30 IU/mL

Complement Level C3 ¹

- Low: <90 mg/dL
- High: > 180 mg/dL

Complement Level C4¹

- Low: < 10 mg/dL
- High: > 40 mg/dL

Immunoglobulin G

- Low: < 6.94 g/L
- Normal/High: ≥ 6.94 g/L

Immunoglobulin A

- Low: < 0.81 g/L
- Normal/High: ≥ 0.81 g/L

Immunoglobulin M

- Low: < 0.48 g/L
- Normal/High: ≥ 0.48 g/L

11.5.5.1. B Cell Subsets

B cell specimens were collected at selected sites which were all Japan sites.

The B cell subsets (as specified in the protocol) include:

- CD20+
- Naïve CD20+/27-
- Memory CD20+/27+
- Activated CD20+/69+
- Plasmacytoid CD20+/138+

¹ The SI unit for C3, C4 is g/L. For analysis, complement levels will be reported in mg/dL. To convert lab values reported as g/L to mg/dL, multiply the lab value by 100.

- SLE subset CD19+/27^{BRIGHT}/38^{BRIGHT}
- Plasma cells CD20-/138+

In addition, the following two B cell subsets have been added to the RAP:

- Concentration of CD19+
- Short-lived plasma subset CD27+BRIGHT/CD20-

Note: the parent study BEL113750 included the analysis of these two additional B cell subsets. However, B cell samples were not analysed for the short-lived plasma subset in the parent study BEL112341; thus, because of missing data at baseline and post-baseline visits for the first 6 months of belimumab treatment (and data for the subsequent 12 months is limited to the placebo group), no summary will be produced for this B cell subset for BEL112341 subjects. However, available short-lived plasma B cell subset data will be listed.

Reporting of B Cells subsets

CD19+, CD20+, naïve and memory B Cell subsets (collectively known as "common B cell" subsets) are reported in counts per microliter (uL). Activated, plasmacytoid, SLE subset, plasma and short-lived plasma b cells (collectively known as "rare B cell" subsets) are reported in counts per millilitre (mL).

Table 16 includes the variables, labels and details of derivations to be used in the reporting of the B cell subsets.

CONFIDENTIAL

BEL114333

Table 16 Variables, labels and details of derivations to be used in the reporting of the B cell subsets

		ADaM Lab Test Code		d/or Conversion of B cell subsets Code (LBTESTCD)
Protocol specified B cell subset	B cell subset label for displays	(LBTESTCD)	BEL114333 and BEL113750 ¹	BEL112341
Common B cells				
CD19+	CD19 (/uL)	CD19	CD19 requires conversion to /uL	CD19 reported as /uL
CD20+	CD20 (/uL)	CD20	CD20 requires conversion to /uL	CDZ037 reported as /uL
Naïve CD20+/27-	Naïve CD19+CD20+CD27- (/uL)	CDX136	CDX136 requires conversion to /uL	CDZ035 reported as /uL
Memory CD20+/27+	Memory CD19+CD20+CD27+ (/uL)	CDX137	CDZ137 requires conversion to /uL	CDZ034 reported as /uL
Rare B cells				
Activated CD20+/69+	Activated CD19+CD20+CD69+ Normalised (COUNT/mL)	CDX141N	CDX155E, CD19E from Plasma Panel and CD19 concentration from TBNK Panel	CDZ005EV, CD19EVC from Plasma Panel and CD19 concentration from TBNK Panel ¹
Plasma CD20-/138+	Plasma CD19+CD20-CD138+ Normalised (COUNT/mL)	CDX143N	CDX143E, CD19E from Plasma Panel and CD19 concentration from TBNK Panel	CDZ007EV, CD19EVC from Plasma Panel and CD19 concentration from TBNK Panel ¹
Plasmacytoid CD20+/138+	Plasmacytoid CD19+CD20+CD138+ Normalised (COUNT/mL)	CDX145N	CDX145E, CD19E from Plasma Panel and CD19 concentration from TBNK Panel	CDZ002EV, CD19EVC from Plasma Panel and CD19 concentration from TBNK Panel ¹
Short-lived Plasma CD27+BRIGHT/CD20-	Short-lived Plasma CD19+CD20-CD27b+ Normalised (COUNT/mL)	CDX154N	CDX154E, CD19E from Plasma Panel and CD19 concentration from TBNK Panel	NA
SLE subset CD19+/27BRIGHT/38BRIGHT	SLE Subset CD19+CD38b+CD27b+Lymph Normalised (COUNT/mL)	CDX156N	CDX156E, CD19E from Plasma Panel and CD19 concentration from TBNK Panel	CDZ024EV, CD19EVC from Plasma Panel and CD19 concentration from TBNK Panel ¹

¹ The derivation for the normalisation of rare B cell subsets should use the CD19 Concentration from the TBNK flow panel. BEL113750 the TBNK method was used but the method was incorrectly reported as PLASMA by the central lab (and cannot be corrected as BEL113750 has met DBF). BEL112341 the method is not specified, but it is confirmed that TBNK was used.

B cell unit conversions and Normalization of Rare B cell Subsets

The Benlysta program standard is to report common B cells (CD19, CD20, naïve and memory) in counts per microliter (uL).

Common B cells are not normalized but they must be converted to uL for reporting. To convert values reported from GI/L (= 10^9 / L) to count per uL (= cells / mm³), multiple the value by 10^3 or 1000.

Example: (0.25 GI/L) x (1000) = 250 / uL

Rare B cell subsets are reported in counts per millilitre (mL). Rare B cell subsets reported in GI/L will be converted to cells / ml using the following formula:

Normalized count/mL = [(rare cell events) / (CD19+ events)] * (CD19+ count/uL) * 1000

Note: the CD19+ B cell event count should be taken from the same flow panel as the B cell subset being converted in the derivation. The CD19+ concentration should be taken from the TBNK panel and converted to count/uL prior to the normalisation and conversion of the rare B cell subset.

Example: Normalization and conversion of Plasma CD20-CD138+ to count/mL

Given:

- Plasma CD20-CD138+ number of events = 16
- CD19+ number of events on Plasma panel = 10250
- CD19+ concentration on TBNK panel = 0.35 GI/L

Then:

Plasma CD20-CD138+ Normalized (count/mL) = (16 / 10250) * (0.35*1000) * 1000 = 546.34 count/mL

11.6. Appendix 6: Premature Withdrawals & Handling of Missing Data

11.6.1. Premature Withdrawals and Completion

Element	Reporting Detail
General	 All subjects were indicated as withdrawn from study BEL114333 based on the design of the end of treatment CRF page. Study completion (i.e. as specified in the protocol) is defined as the subject was still participating in the study at the time belimumab became commercially available in Japan and Korea * or the subject transferred to a different protocol (as indicated by a reason for withdrawal of Investigator Discretion), or upon the decision by the sponsor to close/terminate the study (as indicated by a reason for withdrawal of Study/Closed Terminated).
	 * the study is now being closed as PMDA approved Benlysta, and subjects have been transitioned from study supplied belimumab over to commercially available Benlysta. The KFDA approved Benlysta in 2015. • There will be no adjustments for missing results (i.e. LOCF) due to subject withdrawal prior to study termination. • All subjects are expected to return for an exit visit. Subjects no longer receiving belimumab after their exit visit are expected to return for follow up visits. See Section 2.3 for more details. • All available data will be listed and all available planned data will be included in summary tables and figures, unless otherwise specified.

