4.4. Withdrawal Criteria

A subject may voluntarily discontinue participation in this study at any time. The investigator may also, at his or her discretion, discontinue a subject from this study. Every effort should be made by the investigator to keep subjects in the study and to ensure return for the Exit visit 4 weeks after the last dose of belimumab, and the follow-up visits 16 weeks after the last dose. For any subject who had an anti-belimumab antibody response at the 16-week follow-up visit (or last study visit at which immunogenicity was assessed if the 16-week follow-up immunogenicity sample is not available), an attempt will be made to obtain a serum sample for anti-belimumab antibodies at least 6 months after the last dose of study agent. From subjects at selected sites only, B-cell subsets will be collected at the EXIT visit and at approximately 6 months after the last dose of study agent.

Notwithstanding this requirement, the investigator should adjust concurrent medications as clinically required.

Reasons for subject withdrawal include “adverse event”, “lack of efficacy”, “protocol deviation”, “study closed/terminated”, “lost to follow-up”, “investigator discretion”, and “withdrew consent”. The investigator will record the primary reason in the electronic case report form (eCRF) and any data collected up until the point of withdrawal, and the follow-up visits will be used in the analyses.

If a subject is permanently discontinued from belimumab during the course of the study, the subject must be withdrawn from the study. In addition, subjects will be withdrawn from the study if any of the following criteria are met:

- **Unacceptable toxicity** including:
 - **Laboratory parameters:** Demonstrate clinically important changes in laboratory parameters.
 - **Liver Chemistry:** Detailed in Section 6.3.1.
- **Pregnancy:** Positive urine pregnancy test.
- **Concurrent Medication:** Prohibited concurrent medication or therapy (See Section 5.3.2 and Section 5.3.3).
- **Consent:** Withdrawal of consent.
- **Compliance:** Missed 3 or more consecutive study infusions.

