2. SUMMARY OF KEY PROTOCOL INFORMATION

2.1. Changes to the Protocol Defined Statistical Analysis Plan

Changes from the originally planned statistical analysis specified in the protocol are outlined in Table 1.

Table 1 Changes to Protocol Defined Analysis Plan

Protocol	Reporting & Analysis Plan		
Statistical Analysis Plan	Statistical Analysis Plan	Rationale for Changes	
Study Completion Status	-		
Section 3.1. Study Design Study completion is defined as: IV belimumab becomes commercially available in the respective countries. Upon the decision of the sponsor to close/terminate the study.	Definition has been revised to include "the subject transferred to a different protocol".	The BEL114333 protocol intent was to include this additional criterion. Similar definition is contained within the BEL113750 OL (China only) Phase of the protocol.	
Safety			
Section 8.1.3 Safety The frequency of AEs will be tabulated by treatment groups, according to the treatment assignment during the respective DB phase of study BEL113750 or BEL112341 (C1115).	Although the adverse events in this section were initially intended to be summarised by parent study randomised treatment groups, the safety data will actually be shown as one total belimumab group.	Similar approach to other Long- Term Continuation (LTC) studies, allowing meaningful comparisons between study BEL114333 and the LTC studies.	
Section 8.1.3 Safety The number of subjects with AEs and the incidence rate of AEs will be summarised in each 6-month time interval.	Adverse events will be summarised by year interval.	For consistency with the LTC studies.	
Section 8.1.3 Safety	AE of Special Interest (AESI) will also be summarised.	AESI (serious and non-serious) of scientific and medical interest specific for GSK are being reported across the Benlysta program.	
Section 8. Data Analysis and Statistical Considerations. Immunogenicity and B cell marker data collected at the 6-month post-treatment visit will be reported separately as an addendum to the clinical study report.	Not required.	The data base will be locked once all subjects have completed their last visit of BEL114333. All data will be included in the BEL114333 CSR.	

Protocol Reporting & Analysis Plan		
Statistical Analysis Plan	Statistical Analysis Plan	Rationale for Changes
Efficacy		- tuttonalo loi onango

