4. ANALYSIS POPULATIONS

All Subjects	 Japan and Korea subjects who were randomised in the DB 52-week parent study BEL113750. Additionally, participation in BEL114333 was extended to Japanese subjects in the parent study BEL112341, of which 30 subjects were randomised at the beginning of BEL112341 (but only 27 remained to enter the openportion of BEL112341). A total of 25 of these 27 subjects elected to join BEL114333; the other 2 did not elect to join BEL114333. This population, and all subsequently defined 	Enrolment and Population level displays for patient disposition
	This population, and all subsequently defined	

	populations below, will be based on data from all subjects as one total belimumab treatment group. Additional summaries will be presented by the parent randomised treatment groups. See Section 2.4.1.	
Screened	All subjects in the All Subjects population who completed the parent studies BEL113750 (Japan and Korea) or BEL112341 (Japan only) and were eligible to enrol in BEL114333.	Study Population
Enrolled	All subjects who enrolled in BEL114333.	Disposition-level displays
Safety	All subjects in the Enrolled population who received at least one IV dose of belimumab during BEL114333. Analyses will be based on all available follow-up from the first dose of belimumab treatment through to study end. See Section 2.4. As such exposure data to belimumab will be included for subjects who received their first dose in the parent study, and subsequently enrolled in BEL114333.	Safety/Efficacy analyses and displays
	Note: although the OL analysis for Japan and Korea will be based on the Safety population, the definition is the same as the Efficacy population used for China (which excluded subjects from one site).	

Refer to Appendix 12: List of Data Displays which details the population used for each display.

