6.1. Overview of Planned Analyses

Table 3 provides an overview of the planned study population analyses, with full details of data displays being presented in Appendix 12: List of Data Displays.

Table 3 Overview of Planned Study Population Analyses

Display Type	Data	Data Displays Generated		
	Table	Figure	Listing	
Subject Disposition				
Subject Enrolment (All Subjects Population)	Y [1] [2]			
Enrolment by Site	Y [1]			
Belimumab Treated Subject-Years on Study	Y [3]			
Subject Disposition (All Enrolled Subjects Population)	Y [4]			
Reasons for Study Withdrawal			Y [5]	
Study Completion Status per Protocol	Υ [6]		Y [7]	
Time to Withdrawal Prior to Study Closing	Υ [8]	Y [8]		
Subject Completion Status per Protocol by Year Interval	Υ [9]			
Inclusion/Exclusion Criteria				
Inclusion/Exclusion Criteria Deviations	Y [1]		Υ	
(All Enrolled Subjects Population)	1 1.1		ĭ	
Protocol Deviations				
Subjects with Important Protocol Deviations	Y [1]		Υ	
(All Enrolled Subjects Population)		Ţ		

NOTES:

- T = tables, F = Figures, L = Listings, Y = Yes display generated.
- [1] Summarised by parent randomised treatment group and the total population.
- [2] Summarises No. (%) of Japan and Korea subjects randomised & completed parent study BEL113750, and those subjects who were enrolled and included in the Safety population for BEL114333. Additionally, Japan subjects from BEL112341 are also summarised.
- [3] Summarises person-years and cumulative person-years for time on belimumab treatment by year interval and parent randomised treatment group, and person-years for at any time post-baseline up to a subject's final contact. See Section 11.5.1 for definition of final contact.
- [4] Summarises subject disposition per End of Treatment CRF page as determined by the investigator. Note, the CRF page does not include an option for selecting study completion. Thus, all subjects were indicated as being withdrawn.
- [5] Listing indicates reasons and time of withdrawal per End of Treatment CRF page (see footnote 4).
- [6] Summarises study completion status per protocol (completed, death, withdrawn [and reasons for withdrawal]). See Section 11.6.1 for definition of study completion.
- [7] Listing indicates subject completion status (see footnote 6) and whether subjects are included in analysis populations.

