- [8] Kaplan-Meier plot of time (in days) to withdrawal (see footnote 6 for definition of withdrawal) and associated summary table. See Section 11.5.1 for derivation of time to withdrawal. Note: subjects who died or completed the study per the protocol, will be censored.
- [9] Summarises No. (%) of subjects starting each year interval, and of those, the number completed, died and withdrawn [and reason for withdrawal], or ongoing in the study at the end of that year interval. Will be summarised using frequencies and percent. The denominator for each year will be the number of subjects who started each year of treatment.

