8.1.6. Time to First Severe SFI Flare

SFI flare data are collected at scheduled visits where only one flare may be recorded. The frequency of these flare assessments vary and will be collected in accordance to their respective timings (Section 11.1). Additional flares occurring between scheduled assessments during study BEL114333 were collected using an additional SLE flare log. (Note: only the flare data were collected but no visit information) and flares will be assigned to the next scheduled visit for flares.

Time to the first severe SFI flare during belimumab treatment will be summarised by the parent randomised treatment group, and the total Safety population.

Note, for this study, analyses of SFI flares will be conducted based on the modified SLE flare index (modified excludes severe flares from the SELENA SLEDAI assessment that were triggered only by an increase in SELENA SLEDAI score to > 12, see Section 11.5.4.5).

Only post-baseline flares will be considered in these analyses. Flares (not subjects) occurring on the first belimumab dose date should be removed from the analysis dataset prior to determining the first flare.

Time to the first severe SFI flare is calculated as the number of days from the first dose of belimumab treatment up to the first severe flare event (event date – first dose date of belimumab + 1). The disposition of subjects is defined as follows:

Subject Disposition	Event Met	Event Date
Subject has a severe SFI flare		
Subject has a severe SFI flare during the study	Yes	Date of first severe SFI flare
Subject does not have a severe SFI flare		
Subject withdraws from the study	No	Censored at last available date where flare is assessed
Subject dies during the study	No	Censored at date of death.
Subject who completes the study *	No	Censored at last available date where flare is assessed

^{*} As per the protocol. Includes subjects who transferred to study BEL116027, or who were still participating in the study at the time of the sponsor decision to close the study.

The display will summarise the number and percentage of subjects with a severe SFI flare as well as the Kaplan-Meier estimate of the median, 25th and 75th percentiles of days to first severe SFI flare. For subjects who experienced a severe SFI flare, the display will summarise the median, 25th and 75th percentiles, minimum and maximum time to the first severe SFI flare from baseline, by parent randomised treatment group, and the total Safety population.

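### The only stated marker of completion by transfer is the CRF reason Investigator Discretion, which is also an ordinary withdrawal reason, and no check against enrolment in the receiving study is stated

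*SAP*

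**What the plan says.** Completion status has to be derived, because the End of Treatment page cannot record it. SAP Section 6.1, Table 3, footnote 4 says "Note, the CRF page does not include an option for selecting study completion", so every subject appears there as withdrawn.

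SAP Section 11.6.1 gives three routes to completion:

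- **Commercial availability:** "the subject was still participating in the study at the time belimumab became commercially available in Japan and Korea". No CRF reason is attached to this route.
- **Transfer:** "the subject transferred to a different protocol (as indicated by a reason for withdrawal of Investigator Discretion".
- **Sponsor closure:** indicated by the CRF reason for study closure or termination.

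The transfer route is a SAP addition. The protocol's completion definition (Section 3.1) covers only commercial availability and sponsor decision. SAP Section 2.1, Table 1 discloses the change ("Definition has been revised to include 'the subject transferred to a different protocol") but does not say how a transfer is identified. The footnotes to the flare censoring tables name the receiving study; the one in Section 8.1.6 reads "Includes subjects who transferred to study BEL116027, or who were still participating in the study at the time of the sponsor decision".

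Protocol Section 4.4 puts the same code among its reasons for withdrawal: "lost to follow-up”, “investigator discretion”, and “withdrew consent".

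**The concern.** Investigator Discretion does not mean transfer. Protocol Section 4.4 lets the investigator discontinue any subject at his or her discretion, and the code naturally records that. The protocol describes joining another continuation study as the subject's own choice and lists it separately from withdrawal by the physician (Protocol Summary and Section 3.1). Using the code as the marker for transfer merges two routes that the protocol keeps apart.

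At stake is the account of attrition. Efficacy is summarised on observed cases (SAP Section 11.6.2.2), with no adjustment for results missing after withdrawal (Section 11.6.1). Completion status and time to withdrawal are therefore main guides to how selected the later-year subjects are. Counting an investigator withdrawal as a completion makes retention look better than it was.

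**Working it through.** The plan gives no figure to reproduce, so the check is mainly one of text.

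**1. Does the code match the condition?** For sponsor closure, the CRF reason and the completion criterion mean the same thing. For transfer they do not. Protocol Section 4.4 has no reason meaning transfer, and Investigator Discretion covers any withdrawal the investigator decides on.

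**2. Is there a safeguard elsewhere?** SAP Table 1 states the criterion without an identification rule. The footnotes in Sections 8.1.6, 8.2.6 and 8.2.8 name BEL116027 but give no data source. No section states an enrolment cross-check, a review of free text or a manual adjudication. Section 11.6.1 does not say how to classify an Investigator Discretion exit that was not a transfer.

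**3. Where does the classification go?** Table 3 footnote 6 refers completion status to Section 11.6.1. This feeds Table 1.5, the by-year Table 1.6 and the completion-status listing. Footnote 8 carries it into the time-to-withdrawal analysis (Table 1.7, Figure 2.1), where "subjects who died or completed the study per the protocol, will be censored". If the code alone is taken as proof of transfer, Investigator Discretion could never appear as a withdrawal reason in Table 1.5.

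**4. Where does it not go?** The flare analyses censor withdrawn subjects and completers in the same way, at the last available assessment, so a change of label alters nothing there. Table 1.4 and Listing 2 report the reason as recorded.

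**5. Size per subject, completion percentage.** Shift = 100/N points for each net misclassified subject, where N is the Safety population. N is not stated. SAP Section 4 gives a partial count: "A total of 25 of these 27 subjects elected to join BEL114333". BEL113750 subjects come on top of these, so N > 25, provided the 25 were all dosed.

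| N | Shift per subject (points) |
|---|---|
| > 25 (from the SAP) | < 100/25 = 4.0 |
| 50 (assumed) | 100/50 = 2.0 |
| 100 (assumed) | 100/100 = 1.0 |
| 200 (assumed) | 100/200 = 0.5 |

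With no misclassified subject the shift is 0.

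**6. Size per subject, Kaplan-Meier curve.** If one withdrawal is wrongly censored when r subjects are at risk, the factor (1 − 1/r) drops out of every later estimate of remaining in the study.

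| r (assumed) | Factor lost |
|---|---|
| 20 | 1 − 1/20 = 0.95 |
| 50 | 1 − 1/50 = 0.98 |
| 100 | 1 − 1/100 = 0.99 |

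The subject leaves the risk set at the same time under either label, so no other factor changes.

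**The case against.** The strongest reply is that the bracket is not the criterion. The stated condition is that the subject transferred; the bracket only explains how transfers appear in a CRF that has neither a transfer reason nor a completion option. On that reading, an Investigator Discretion exit who did not transfer fails the condition. Table 1 and the flare footnotes support this, since they speak of transfer without mentioning the code. Timing fits too: SAP Section 3.2 dates the last subject visit in Japan to 13 September 2018, and Section 11.6.1 describes the coding in the past tense, so the authors may be reporting what they saw in the data. Being listed in Protocol Section 4.4 also does not by itself mark a reason as non-completion, because study closure is on the same list and counts as completion. Finally, the CRF page and table shells are not part of the documents, so a check may exist that the SAP text does not mention.

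Much of this stands. The text does not show that any subject was miscounted, and the descriptive reading is possible. It does not remove the gap, however. Section 11.6.1 is where the derivation is specified, and it gives a programmer no other rule. If the descriptive reading is intended, the SAP still needs to say what establishes a transfer. Table 1.4 and Listing 2 let a reader count the Investigator Discretion exits, and so bound the problem, but not separate transfers from other investigator withdrawals.

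**Conclusion.** The concern holds, as a minor point. The SAP's only stated indicator of completion by transfer is a reason the protocol uses for general investigator withdrawals, and no check against the receiving study is specified. A non-transfer exit under that code that meets no other criterion would add one to completion and remove one event from the time-to-withdrawal display; a transfer coded otherwise could do the reverse.

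The shift per net misclassified subject is under 4.0 percentage points of completion, and 2.0 to 0.5 points for an assumed N of 50 to 200. The lost Kaplan-Meier factor is 0.95 to 0.99 for an assumed 20 to 100 subjects at risk. The number of such subjects is unknown and may be zero. The commercial-availability route carries no code and is unaffected, as are the flare analyses. Only descriptive disposition displays are reached.

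**What to change.** In SAP Section 11.6.1, define completion by transfer as documented enrolment in another belimumab protocol (for example BEL116027), whatever CRF reason was recorded. State that remaining Investigator Discretion exits are withdrawals, and events in the time-to-withdrawal analysis, unless they meet one of the other two completion criteria (still participating at commercial availability, or sponsor closure).

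The cost is about one sentence in the SAP and one cross-check of Investigator Discretion exits and recorded transfers against enrolment in the receiving protocol. Reported completion may come out slightly lower.
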